## 7 Trial procedures

### 7.1 Pre-treatment Assessments

#### 7.1.1 Screening – Cohorts 1 and 2

The results from the following routine procedures may be used to assess the participant's eligibility. Where routine results are not available at the time of consent, the procedure(s) will be carried out after consent. All must have been done within 24 hours prior undertaken as part of their standard care before their first dose of rtPA. These will also constitute the baseline assessments for cohort 2.

Patients receiving rtPA and SOC will undertake all assessments:

- Informed consent
- Demographics
- Review of medical history (including inpatient history and COVID-19 diagnosis – see section 7.7).
- Eligibility review
- Pregnancy test (blood or urine) for female participants of childbearing potential
- Concomitant medications
- Directed physical examination including vital signs (heart rate, temperature, blood pressure, and body weight)
- Documentation of respiratory status: Respiratory status of patients is monitored hourly and data points will be extracted for every four hour where available, but one data point is required as a minimum. The time of measurement should be documented. The variables include:
  - Details of oxygen and respiratory support including the type of device and FiO2  
Respiratory rate
  - PaO2
  - For IMV patients, details of ventilation including but not exclusively the below
    - Tidal volume (in mL)
    - Full sedation or not – not for cohort 2
    - Paralysis or not – not for cohort 2
    - Patient position – not for cohort 2
    - Peak inspiratory pressure (for computing compliance)
    - PEEP (for computing compliance )

- For non-invasive support patients:
  - SpO2
  - Oxygen flow rate
  - National Early Warning Score (NEWS 2) – not for cohort 2
- For CPAP patients
  - Positive end expiry pressure (PEEP)
- Local blood testing as per section 7.6.2
- Research blood sampling as per section 7.6.2
- Clinical status as assessed by 7-point ordinal scale (see section 7.7)
- Sequential Organ Failure Assessment (SOFA) score (see section 7.7)
- Glasgow coma scale (see section 7.7)

### **7.1.2 Baseline assessments (for duration of 3 days prior to treatment) – Cohort 1 only**

Screening assessments will be combined with daily routine assessments taken from the 3 days prior to dosing to establish a baseline:

- Documentation of respiratory status: Respiratory status of patients is monitored hourly and data points will be extracted for every four hours where available, but one data point is required as a minimum. The time of measurement should be documented. The variables include:
  - Mode of Ventilation
  - Oxygenation index
  - Respiratory rate
  - PaO2
  - SpO2
  - FiO2
  - For IMV patients, details of ventilation including but not exclusively the below
    - Tidal volume (in mL)
    - Full sedation or not
    - Paralysis or not.
    - Patient position
    - Peak inspiratory pressure (collected for computing compliance)
    - PEEP (collected for computing compliance)
  - For non-invasive oxygen support patients:
    - National Early Warning Score (NEWS 2)
  - For CPAP patients
    - Positive end expiry pressure (PEEP)
- Clinical status as assessed by 7-point clinical ordinal scale (see section 7.7)
- Sequential Organ Failure Assessment (SOFA) score (see section 7.7)
- Glasgow coma scale (see section 7.7)

## **7.2 Registration Procedures**

Participant registration will be undertaken by the coordinating trial team at site on a trial specific registration form.

Participants are considered to be enrolled into the trial following: consent, pre-treatment assessments (see section 7.1), confirmation of eligibility, completion of the registration process, allocation of the participant trial number.

### 7.3 Treatment Schedule for nebulisation

Patients in the rtPA and SOC group will receive the first dose as soon as possible after enrolment, and in accordance with the dosing schedule below. The time of initiation of the first dose will be recorded and the timing of the initiation of subsequent doses will be relative to this time. 10mg rtPA will be administered by nebulisation every 6 hours. Treatment with rtPA will be administered at a dose of 10 mg every 6hrs for a minimum of 5 days initially and a maximum of 14 treatment days overall.

#### 7.3.1 Cohort 1

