## 4 Trial design

### 4.1 Overall design

This is a phase II, open label, single centre, uncontrolled, repeated dose, pilot trial of nebulised rtPA in patients with COVID-19 ARDS.

The study will recruit patients requiring either IMV or non-invasive oxygen support. Eligible patients (or if patients lack capacity, their legal representative) will be provided with an information sheet and informed consent will be sought (see section 6.3). Eligibility will be assessed via routine clinical assessments, which may have been done prior to consent. The only exceptions are a pregnancy test (blood or urine), and possibly any assessments listed in section 7.1 that were not done as per routine care. These must be done following consent, and all screening assessments must have been done during the 24-hour period before dosing with rtPA.

The study will run two cohorts sequentially. In cohort 1, 9 consented patients received nebulised rtPA in addition to SOC. 6 patients were receiving IMV and 3 were receiving non invasive support with NIV or CPAP or high flow oxygen or standard oxygen therapy. As an observational arm, matched historical controls who received standard of care were also recruited at a ratio of 2 controls to every 1 treatment arm patient, resulting in 18 historical controls. Originally, the study aimed to recruit 12 patients with 6 on each ventilation type (IMV and non-invasive oxygen support). This would have resulted in 24 historical controls. After the first wave of COVID-19 cases decreased in August 2020 in the UK it became difficult to continue recruitment, so recruitment closed for cohort 1.

With a second surge underway in early 2021, cohort 2 will aim to recruit more patients during this period to provide more data on the safety of rtPA. Based on the analysis of cohort 1, fewer timepoints will be collected (see sections 7.1.2 and 7.5.2), which will allow for more rapid recruitment while at the same time not compromising safety monitoring. A more flexible dosing regimen for rtPA will be utilised which is described in section 7.3.2. 30 patients will be recruited in total, with an aim to recruit a minimum of 10 IMV patients and 10 patients on non-invasive oxygen support.

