A statistically powered randomised controlled trial (RCT) would be ideal to define the magnitude of benefit and impact on overall survival and is the typical design in patients with ARDS. Although there is clinical data on the safety of nebulised rtPA, but there is no clinical data in this clinical condition to facilitate a sample size calculation. There is data from a small RCT that has used another fibrinolytic agent, but the doses are not comparable(Abdelaal Ahmed Mahmoud et al. 2020). When a patient is randomised to receive no treatment, this precludes participation in other interventional studies which might decrease the risk of mortality. The most recent figures suggest a 50% mortality in patients receiving IMV there is 50% mortality. ([https://www.icnarc.org/About/Latest-News/2020/04/04/Report-Protocol-Version 10.0 dated 2 Feb 2021](https://www.icnarc.org/About/Latest-News/2020/04/04/Report-Protocol-Version-10.0-dated-2-Feb-2021))

On-2249-Patients-Critically-Ill-With-Covid-19) Currently there is a concerted effort to introduce multiple therapies based on our understanding of the pathophysiologic basis of disorder. Further, if this pilot study shows significant effect in a subset of patients, there would be justification to progress to a statistically powered RCT. We would progress to a RCT only after submission of a substantial amendment to this trial protocol or submission of a new clinical trial application. In the event of major adverse drug reactions or minor improvement in the oxygenation as assessed by  $\text{PaO}_2/\text{FiO}_2$ , there are minimal gains to be had with a larger randomised control study.

[figure not shown]
For patients in the rtPA group, 10 mg of rtPA dissolved in 5 ml of diluent will be given every 6 hrs for a maximum of 14 treatment days. Efficacy will be assessed by the monitoring of arterial oxygen saturation.

Safety monitoring will be performed by assessment of the incidence and severity of bleeding events, and by the monitoring of plasma fibrinogen levels and routine coagulation parameters. Additional samples will be taken for exploratory assessment of potential biomarkers, including (but not restricted to) PAI- 1, alpha 2 antiplasmin and a range of inflammatory cytokines and coagulation proteins. All other monitoring will be done as per SOC. From the end of the treatment phase both groups will be followed up in accordance with SOC.

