### **5.3 Storage and handling of IMP(s) at site**

All IMP aspects of the trial at participating sites are the responsibility of the PI, who may delegate this duty to the local pharmacist or other appropriately trained personnel. The delegation of duties must be recorded on the Staff Signature and Delegation of Tasks.

Storage must be in the original package in order to protect from light. Do not store above 25 °C. Actilyse will be reconstituted with water for injection in accordance with the instructions in the Summary of Drug Arrangements (SoDa) for the trial.

The reconstituted solution has been demonstrated to be stable for 24 hours at 2 °C – 8 °C and for 8 hours at 25 °C. From a microbiological perspective, the product should be used immediately after reconstitution. If not used immediately, in-use storage times and conditions prior to use are the responsibility of the user and would normally not be longer than 24 hours at 2 to 8°C.

For cohort 1, 10 mg of Actilyse reconstituted in 5ml of diluent provided will be used in an ultrasonic nebuliser available in the hospital. For cohort 2, 20mg will be reconstituted as directed in the SoDa, and will be used in an ultrasonic nebuliser available in the hospital.

Detailed instructions are contained in the summary of drug arrangements.

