#### rtPA treatment schedule for IMV patients

Study Day	Time (hours)	Dose No.	Dose (mg)	Daily Dose (mg)
1	0	1	20	60
	8 ( $\pm$ 2hrs)	2	20	
	16 ( $\pm$ 2hrs)	3	20	
2	24 ( $\pm$ 2hrs)	4	20	60
	32 ( $\pm$ 2hrs)	5	20	

	40 ( $\pm$ 2hrs)	6	20	
3	48 ( $\pm$ 2hrs)	7	20	60
	56 ( $\pm$ 2hrs)	8	20	
	64 ( $\pm$ 2hrs)	9	20	
4	72 ( $\pm$ 2hrs)	10	20	60
	80 ( $\pm$ 2hrs)	11	20	
	88 ( $\pm$ 2hrs)	12	20	
5 to 14	Patients will continue to be dosed every 8 hours (<math>\pm</math> 2hrs) from the time of the first dose, resulting in 42 doses in total being administered.			

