#### **rtPA treatment schedule for patients on non-invasive oxygen support**

This dosing schedule will consist of a higher loading dose for the first 2 days.

Study Day	Time (hours)	Dose No.	Dose (mg)	Daily Dose (mg)
1	0	1	20	60
	8 ( $\pm$ 2hrs)	2	20	
	16 ( $\pm$ 2hrs)	3	20	
2	24 ( $\pm$ 2hrs)	4	20	60
	32 ( $\pm$ 2hrs)	5	20	
	40 ( $\pm$ 2hrs)	6	20	
3	48 ( $\pm$ 4hrs)	7	20	40
	60 ( $\pm$ 4hrs)	8	20	

4	72 ( $\pm$ 4hrs)	9	20	40
	84 ( $\pm$ 4hr)	10	20	
5	96 ( $\pm$ 4hr)	11	20	40
	108 ( $\pm$ 4hr)	12	20	
6 to 14	Patients will continue to be dosed every 12 hours (<math>\pm</math> 4hrs) from the time of the first dose, resulting in 30 doses in total being administered.			

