b Local blood testing as per section 7.6.2 are to be done at a minimum once a day for cohort 1, or every other day for cohort 2, until 5 days after the last dose, and then as required until day 28, discharge or death whichever occurs first.

c Research blood sampling will be done once at baseline at 48 hours (+/- 24 hours), 96 hours (+/- 24 hours), and then twice weekly as per section 7.6.2. Twice weekly testing should be evenly spaced across weekdays if possible.

d Dosing schedule as per section 7.3

e End of study data will be collected at day 28, discharge or death whichever occurs first as per section 7.5.

f to be taken where available once daily for 3 days prior to dosing (cohort 1 only). Screening assessments can be used as part of this baseline period.

**21 Appendix 2 - Lookup table for imputed PaO2 for a given SpO2 based on non-linear equation (from Brown SM et al. Nonlinear Imputation of PaO2/FIO2 From SpO2/FIO2 Among Mechanically Ventilated Patients in the ICU: A Prospective, Observational Study. Crit Care Med. 2017; Aug;45(8):1317-1324)**

Measured SpO 2 (%)	Imputed PaO 2 (mmHg)
100*	167*§
99*	132*
98*	104*
97*	91*
96	82
95	76
94	71
93	67
92	64
91	61
90	59
89	57
88	55
87	53
86	51
85	50

Measured SpO 2 (%)	Imputed PaO 2 (mmHg)
84	49
83	47
82	46
81	45
80	44
79	43
78	42
77	42
76	41
75	40
74	39
73	39
72	38
71	37
70	37

\*Generally considered unreliable on the basis of the sigmoidal shape of the haemoglobin-oxygen dissociation curve

§Based on SpO2 99.5%.

Imputed values calculated using the following equation:

$$PO_2 = \left\{ \frac{\frac{11,700}{(1/S - 1)} + \left[ \frac{50^3}{11,700} \left( \frac{11,700}{1/S - 1} \right)^{1/3} + \left( \frac{11,700}{1/S - 1} \right)^2 \right]^{1/2}}{\left( \frac{11,700}{1/S - 1} \right)^{1/3}} \right\}^{1/3}$$

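### In the cohort 2 non-invasive schedule, doses 6 and 7 (20 mg each) can both be on time only 2 h apart, against a planned 8 h

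*Protocol*

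**What the plan says.** Section 7.3 takes the start of the first dose as time zero and says "the timing of the initiation of subsequent doses will be relative to this time. 10mg rtPA will be administered by nebulisation every 6 hours". By the first part of that text, windows are anchored to the first dose and not to the dose before.

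Section 7.3.2 then gives two cohort 2 tables, with 20 mg per dose in both:

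- **IMV:** every 8 h throughout. Each dose after the first has ±2 h, including dose 7 at 48 h.
- **Non-invasive oxygen support:** every 8 h for doses 1 to 6 (0 to 40 h), with ±2 h after the first. From dose 7 at 48 h the doses are 12 h apart, each with ±4 h.

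The version history entry for version 10.0 says that the window was widened from 2 h to 4 h for twice-daily dosing. Sections 2.5 and 7.4 require a patient whose ventilation type changes to move to the other schedule. Neither says how the first dose after the move is timed. Neither document states a minimum interval between doses.

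**The concern.** Dose 7 is the first dose of the twice-daily phase and has that phase's ±4 h window. The interval leading up to it is still the 8 h step of the loading phase. A window sized for 12 h spacing has been applied to an 8 h gap, and the previous dose may itself be 2 h late. This looks like a side effect of the version 10.0 change. Nothing in the protocol suggests that a gap this short was chosen.

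The tables are what bedside staff follow. Section 6.2 lets trained nurses give the nebulisations. Two doses 2 h apart deliver 40 mg, which is cohort 1's full daily dose. Section 2.6 links the risk of pulmonary haemorrhage to plasmin generated in the alveoli, which depends in part on the amount of rtPA inhaled.

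Cohort 2 also has fewer safeguards than cohort 1. The exclusions for bleeding disorders and recent active bleeding are gone, the fibrinogen threshold at screening falls from 2.0 to 1.5 g/L, and local blood tests are required every other day instead of daily.

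**Working it through.** **Reproducing the protocol's dose counts.** Fourteen days is 336 h.

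- Non-invasive: 6 doses from 0 to 40 h, then (336 − 48)/12 = 24 doses, so 30. The table says "resulting in 30 doses in total being administered".
- IMV: 336/8 = 42. The table says "resulting in 42 doses in total being administered".
- Cohort 1: 336/6 = 56, as its table states.

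All three agree, so the schedules are being read as intended.

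**Shortest on-time gap between consecutive doses.** The formula is (later time − its window) − (earlier time + its window).

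| Schedule and pair | Calculation | Minimum gap |
|---|---|---|
| Cohort 1, all pairs | 6 − 1 − 1 | 4 h |
| IMV, dose 1 to 2 (no window at time 0) | (8 − 2) − 0 | 6 h |
| IMV, all other pairs | 8 − 2 − 2 | 4 h |
| Non-invasive, dose 1 to 2 | (8 − 2) − 0 | 6 h |
| Non-invasive, doses 2 to 6 | 8 − 2 − 2 | 4 h |
| **Non-invasive, dose 6 to 7** | **(48 − 4) − (40 + 2) = 44 − 42** | **2 h** |
| Non-invasive, dose 7 onward | 12 − 4 − 4 | 4 h |

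The three tables contain 55 + 41 + 29 = 125 consecutive pairs. Within its own table, dose 6 to 7 is the only pair below 4 h. Its longest on-time gap is 52 − 38 = 14 h.

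**Patients who switch schedule.** Suppose the new table is also counted from the first rtPA dose, which the protocol does not say. An IMV dose is due at 56 h. The non-invasive dose at 60 h ±4 h may be given from 60 − 4 = 56 h. A patient dosed at 56 h who then switches could meet a window that is already open. The 4 h minimum therefore holds within each table but not across a switch.

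**Checking the repair.** If dose 7 may be given from 46 to 52 h:

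- dose 6 to 7: 46 − 42 = 4 h
- dose 7 to 8: (60 − 4) − 52 = 4 h

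**The case against.** The strongest reply is that this is a corner case. The planned interval is 8 h. A 2 h gap needs dose 6 to be a full 2 h late and dose 7 a full 4 h early, and it can arise at one transition per patient. The wider window was a deliberate amendment, and IMV patients never enter a twice-daily phase, so the ±2 h in their table is an imperfect comparator. All of this stands.

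The protocol also gives reasons to expect low systemic risk. Circulating tPA has a half-life of 5 to 8 minutes (2.6), and cohort 1 showed no evidence of significant absorption (2.7.4), though at 10 mg doses. Licensed intravenous dosing is about 0.9 to 1.2 mg/kg over 1 to 2 h. At an assumed 70 kg that is 63 to 84 mg, against 40 mg nebulised here. Cumulative exposure barely moves: doses 4 to 7 (80 mg) can fall within 46 − 26 = 20 h if dose 7 is held to 46 h or later, and within 44 − 26 = 18 h as written. These points bear on systemic bleeding. They do not settle the local pulmonary effect.

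A reader might infer four stronger things that the documents do not support:

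- **That a 2 h gap is harmful.** No minimum safe interval is given, so harm is not shown.
- **That this is the shortest gap possible anywhere in the trial.** The switching rule prevents that claim.
- **That such a pair would go unrecorded as a deviation.** It would be within window, but neither document gives a rule for logging dose-timing deviations.
- **That the cohort 2 regimen is undetermined.** Section 4.1 says "10 mg of rtPA dissolved in 5 ml of diluent will be given every 6 hrs for a maximum of 14 treatment days" without naming a cohort, section 7.3 does the same, and Appendix 1 places rtPA under a 6-hourly column. But section 4.1 also says "A more flexible dosing regimen for rtPA will be utilised which is described in section 7.3.2", section 5.3 says "For cohort 2, 20mg will be reconstituted as directed in the SoDa", section 2.5 gives the cohort 2 doses, and the Appendix 1 footnote reads "Dosing schedule as per section 7.3". The intended regimen can be worked out.

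**Conclusion.** The point holds for one dose pair in one table. As written, two 20 mg doses 2 h apart meet the cohort 2 non-invasive schedule, a quarter of the planned 8 h and half the minimum for any other pair within its own table. It affects non-invasive patients still on treatment at hour 48; at least 10 patients are planned for that group.

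The conclusion assumes that windows run from the first dose, as section 7.3 says, and that no minimum interval is set elsewhere. The summary of drug arrangements, to which section 5.3 refers for detailed instructions, is not among the documents and could contain one. The case for change is that an apparently unintended allowance sits in an operative dosing table for a fibrinolytic drug and is almost free to remove. It does not rest on demonstrated harm.

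**What to change.** In the cohort 2 non-invasive table, allow the hour-48 dose no earlier than 46 h. A window of 46 to 52 h keeps the late-side flexibility that version 10.0 introduced.

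Also state in 7.3.2 that consecutive doses must start at least 4 h apart, including after a change of schedule, and that this rule overrides the window where the two conflict. Narrowing the one window does not by itself protect patients who switch, so the second sentence is needed.

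The cost is one table cell and one sentence at the next amendment, and slightly less timing flexibility. As separate editorial tidying, the same amendment could add cohort 1 labels to the 10 mg sentences in 4.1 and 7.3 and label the rtPA row of Appendix 1 by cohort.

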##### rtPA treatment schedule

Study Day	Time (hours)	Dose No.	Dose (mg)	Daily Dose (mg)
1	0 ( $\pm$ 1hr)	1	10	40
	6 ( $\pm$ 1hr)	2	10	
	12 ( $\pm$ 1hr)	3	10	
	18 ( $\pm$ 1hr)	4	10	
2	24 ( $\pm$ 1hr)	5	10	40
	30 ( $\pm$ 1hr)	6	10	
	36 ( $\pm$ 1hr)	7	10	
	42 ( $\pm$ 1hr)	8	10	
3	48 ( $\pm$ 1hr)	9	10	40
	54 ( $\pm$ 1hr)	10	10	
	60 ( $\pm$ 1hr)	11	10	
	66 ( $\pm$ 1hr)	12	10	

4	72 ( $\pm$ 1hr)	13	10	40
	78 ( $\pm$ 1hr)	14	10	
	84 ( $\pm$ 1hr)	15	10	
	90 ( $\pm$ 1hr)	16	10	
5	96 ( $\pm$ 1hr)	17	10	40
	102 ( $\pm$ 1hr)	18	10	
	108 ( $\pm$ 1hr)	19	10	
	114 ( $\pm$ 1hr)	20	10	
6 to 14	Patients will continue to be dosed every 6 hours (<math>\pm</math> 1hr) from the time of the first dose, resulting in 56 doses in total being administered.			

The duration of therapy can be extended from five days to a maximum of 14 treatment days in total. This decision can only be made in the absence of any dose-limiting toxicity. Treatment cannot be given for more than 56 doses.

### 7.3.2 Cohort 2

The treatment schedule will differ depending on the ventilation type

#### rtPA treatment schedule for IMV patients

Study Day	Time (hours)	Dose No.	Dose (mg)	Daily Dose (mg)
1	0	1	20	60
	8 ( $\pm$ 2hrs)	2	20	
	16 ( $\pm$ 2hrs)	3	20	
2	24 ( $\pm$ 2hrs)	4	20	60
	32 ( $\pm$ 2hrs)	5	20	

	40 ( $\pm$ 2hrs)	6	20	
3	48 ( $\pm$ 2hrs)	7	20	60
	56 ( $\pm$ 2hrs)	8	20	
	64 ( $\pm$ 2hrs)	9	20	
4	72 ( $\pm$ 2hrs)	10	20	60
	80 ( $\pm$ 2hrs)	11	20	
	88 ( $\pm$ 2hrs)	12	20	
5 to 14	Patients will continue to be dosed every 8 hours (<math>\pm</math> 2hrs) from the time of the first dose, resulting in 42 doses in total being administered.			

#### **rtPA treatment schedule for patients on non-invasive oxygen support**

This dosing schedule will consist of a higher loading dose for the first 2 days.

Study Day	Time (hours)	Dose No.	Dose (mg)	Daily Dose (mg)
1	0	1	20	60
	8 ( $\pm$ 2hrs)	2	20	
	16 ( $\pm$ 2hrs)	3	20	
2	24 ( $\pm$ 2hrs)	4	20	60
	32 ( $\pm$ 2hrs)	5	20	
	40 ( $\pm$ 2hrs)	6	20	
3	48 ( $\pm$ 4hrs)	7	20	40
	60 ( $\pm$ 4hrs)	8	20	

4	72 ( $\pm$ 4hrs)	9	20	40
	84 ( $\pm$ 4hr)	10	20	
5	96 ( $\pm$ 4hr)	11	20	40
	108 ( $\pm$ 4hr)	12	20	
6 to 14	Patients will continue to be dosed every 12 hours (<math>\pm</math> 4hrs) from the time of the first dose, resulting in 30 doses in total being administered.			

### 7.3.3 Treatment discontinuation

Treatment may be stopped at any point in a patient if any of the following rules are met:

- If plasma fibrinogen levels fall to <1.0 g/L, the further dosing of rtPA in the patient will be stopped (see section 7.4).
- Patient maintains saturation on room air that is either normal or normal for them for 48 hours as assessed by the investigator
- A trial stopping rule has been met (see section 7.10)

### 7.3.4 Re-treatment with rtPA after treatment discontinuation due to improvement in patient saturation (as described above)

If there is a recurrence of COVID-19 ARDS related symptoms or a worsening of PaO2/FiO2 ratio, which the investigator considers could be related to treatment discontinuation, treatment can be restarted. The decision to re-treat will be made within 5 days (120 hrs) from the last dose of treatment. Treatment may not be restarted more than once.

The rationale for restarting of treatment must be documented in the notes, along with the absence of toxicity. The patients monitoring will done according to main treatment phase.

### 7.3.5 Re-treatment of patients previously consented and treated on the trial – Cohort 1

For patients that have already been treated under the previous 3 day dosing schedule, if they remain eligible for the trial, they will be offered the option to continue treatment as above – the maximum number of days of extra treatment for these patients will be 11 days. Patients (or their legal representatives) must give consent to this re-treatment.

The total duration of trial participation for these patients may exceed 28 days (to approximately 5-6 weeks) to allow us to extend treatment to the maximum 14 days and to allow us to collect 5 days of post treatment data. We will inform the patient or their legal representative of this possibility and this will be documented in the patient information sheet.

